10.0 STATISTICAL/ANALYTIC CONSIDERATIONS

10.1 Introduction

10.1.1 Paradata Metrics

We will measure temporal engagement by examining users' visits to the app and time spent on app using HMP's paradata timestamps at each login and logout. The paradata will also include information allowing us to link engagement for users who create, like, read, or otherwise interact with content in the app. We will also calculate scores for each participant based on their levels of "active" (posting, commenting) and "passive" (reading) engagement. Active engagement scores will be calculated by assigning one point for each time a participant posted or commented on app content. Passive engagement scores will be calculated using the paradata database to assign a participant one point for each time they read content. Aggregate engagement scores for each participant will be included as indicators and latent factors, as appropriate, in our analyses. This strategy will allow us to examine how different forms of engagement (e.g., temporal engagement, active engagement, passive engagement) influence our study outcomes.

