10.3.2.2 Qualitative Analyses

Using our latent class analysis of users' engagement profiles (e.g. high/low users, lurkers), we will select a subsample of up to 45 enrolled participants (approximately 5 from control and 20 per each intervention arm) across different sociodemographic and user engagement profiles to complete qualitative evaluation interviews (described above in section 5.4.5) Study staff, under the guidance of [name], will create a codebook of *a priori* and emergent themes including operational definitions of all codes and sample quotations to illustrate how to apply each code. Two study team members will use the codebook to independently code the data while a third team member will review these coded sections and resolve discrepancies. We will use Dedoose and Excel matrices to assist with theme identification, coding textual data, and describing relationships among codes (via code co-occurrence and memoing functions).²²¹ Analysis results will be used in conjunction with participants' survey responses, biological outcomes, and usage profiles to present a mixed methods intervention results analysis.

10.3.3 Specific Aim 3:

Specific Aim 3 is to examine whether changes in intersectional stigma and YBLMT's improvements across the HIV care continuum differ based on the network structure underlying user engagement in the two versions of HMP Stigma. To understand the role of social network dynamics between the two intervention conditions, we will compute social network parameters (e.g., size, density, centrality) for each version using the statnet and igraph packages in R.²²² Paradata indicators of active engagement (e.g., forum replies/likes) and passive engagement

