(e.g., reading forum posts) will be used to model threaded engagement networks between users. We will use these structures to describe types of users (e.g., discussion starters, contributors, lurkers), their location within the network (e.g., centrality), the frequency of exchanges between users (e.g., reciprocity), and presence of subgroups (e.g., cliques). Core social network metrics will be computed at the participant-level (e.g., centrality; popularity), as well as by stigma-related topic (e.g., trending, liked). We will use these network parameters to model (1) user engagement in HMP and (2) changes in HIV care continuum outcomes. We will use the general framework of generalized linear mixed models^{101–103} (GLMM) to model these longitudinal outcome trajectories. 110-112 Given that some of our outcomes are binary, some count and some continuous traits they will be treated differently (identity for continuous outcome, logit for binary outcome and natural log for count outcomes). We will use the estimated network parameters as covariates in our models, measuring how network characteristics are associated in differences in outcomes across the two treatment groups. In addition, GLMM also allows us to link YBLMT's individual trajectories with social network changes by adding them as time-varying covariates. For example, one analysis will examine how changes in networks' characteristics effect changes in YBLMT's VS, after adjusting for changes in stigma. These follow a network autocorrelation metric, whereby a term is added to the general model to captures a (weighted) average of peers' outcomes. Exploratory analyses will determine if random effects should be included. Maximum likelihood estimation will be used for fixed effects. To ensure robustness, we will also apply an exchangeable working correlation structure to its corresponding generalized estimating equation model. 104

Note: Any deviations from the analysis plans outlined above or in the sections that follow will be documented and justified in the Statistical Analysis Plan developed for this protocol.

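### Aim 3's model of user engagement uses network predictors counted from the same replies and reads as the engagement scores, so an association is expected even with no peer influence

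*Combined protocol and SAP*

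**What the plan says.** Section 10.3.3 (Specific Aim 3) constructs the networks from engagement paradata. It names "Paradata indicators of active engagement (e.g., forum replies/likes) and passive engagement", with reading of forum posts as the example of the latter, and says these "will be used to model threaded engagement networks between users". Centrality, popularity and similar metrics are computed for each participant. Then: "We will use these network parameters to model (1) user engagement in HMP and (2) changes in HIV care continuum outcomes".

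Section 10.1.1 (Paradata Metrics) defines engagement. For the active score: "Active engagement scores will be calculated by assigning one point for each time a participant posted or commented on app content". For the passive score, the database will "assign a participant one point for each time they read content". A third form, temporal engagement, uses "visits to the app and time spent on app".

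The network parameters may enter as time-varying covariates. Section 10.3.3 states no lag and no separate measurement windows, does not remove a user's own outgoing acts, and does not adjust for earlier engagement. Whether to include random effects is left to exploratory analysis. Section 10.3.3 words the covariate analysis as association, but the Study Abstract speaks of network structures influencing engagement over time, and section 5.4.1 of network composition affecting it.

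**The concern.** A user who replies and reads a lot has many outgoing ties and, from the same log entries, a high engagement score. A user who posts a lot also attracts replies, likes and reads, so incoming ties rise with the user's own posting. Model (1) would then show that network position predicts engagement in either arm, whether or not anyone is influenced by a peer. At stake is a near-certain positive result being read as evidence that network structure drives engagement.

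**Working it through.** The plan gives no power, effect size or activity distribution for Aim 3, so there is no figure of its own to reproduce. The check has three steps.

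**1. Which acts are shared.** For one user in one window, let T = threads started, C = forum replies, L = likes given, R = forum reads, and K = comments on or reads of non-forum content.

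- Active plus passive score (10.1.1): S = T + C + R + K
- Ties sent (10.3.3): D = C + L + R
- Shared: C + R. Only in the score: T and K. Only in the ties: L, because likes are not named as points in 10.1.1.

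The overlap is partial but large when reads dominate. Ties received share no log entry with S in this way. They rise with T, which is part of S.

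**2. Size for ties sent, in closed form.** Assumed means per window: 6 threads, 6 replies, 10 likes, 40 reads (all forum, K = 0). Then mean S = 6 + 6 + 40 = 52, mean D = 6 + 10 + 40 = 56, shared = 6 + 40 = 46. With Poisson counts and a personal activity multiplier with coefficient of variation c:

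corr(S, D) = (46 + 52·56·c²) / √[(52 + 52²c²)(56 + 56²c²)]

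- c = 0 (identical users): 46 / √(52·56) = 46 / 53.96 = 0.85
- c = 0.5: (46 + 728) / √(728·840) = 774 / 782.0 = 0.99
- c = 1: (46 + 2912) / √(2756·3192) = 2958 / 2966.0 = 1.00

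Even with identical users, shared counting alone gives 0.85.

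**3. Null simulations.** Network sizes came from the protocol: Arm 1, 150 + 150 = 300 (section 3.2); Arm 2, 150 + 300 = 450 (section 5.1). No user's activity depended on a peer, and ties went to users in proportion to their posting. Same-window results against the combined score S, with the rates above:

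| Metric | c = 0 | c = 0.5 to 1 | Significant at 5% |
|---|---|---|---|
| Ties sent | 0.85 | 0.99-1.00 | 100% of runs |
| Ties received | about 0.32 | 0.78-0.93 | 100% |
| Eigenvector centrality | about 0.57 | 0.94-0.98 | 100% |

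Simulations with lognormal activity (SD 0.8 and 1.2) gave correlations with the active score of 0.67-0.86 for ties received and 0.88-0.94 for ties or replies sent.

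Time on app behaves differently. With identical users it was significant in 2-7% of runs, near nominal. With c = 0.5 to 1 it was significant in 100% (correlation 0.69-0.98), purely because active users do more of everything.

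**Partial remedies, under the same null:**

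- Lag alone, with stable personal activity: still 100% false positives.
- Lag plus adjustment for own prior engagement: ties received 5-6% in one set of simulations and 15-22% in another; eigenvector centrality 6-19%; ties sent 42-91%.
- Ties received in one window, non-forum engagement in the next, person fixed effects: about 5-6% if each user's activity is fixed, but 93-98% if users drift at different rates and 45-75% if activity fluctuates independently between windows.

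**The case against.** Section 10.3.3 never defines the engagement outcome of model (1). Section 10.1.1 lists visits and time on app first, and these are not counted from ties. New threads and Knowledge Center reads score points without forming a forum tie, while likes do the reverse. With identical users, ties received did not predict the passive score (3-6% of runs). All of this stands. A reader might infer that the plan simply regresses a count on itself; the documents do not go that far, because the outcome is left open and the overlap is partial.

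A reader might also infer that Aim 3 as a whole fails, or that the two network types cannot be compared. The documents do not support that. The Study Abstract, section 2.2 and the opening of section 10.3.3 define Aim 3 chiefly by stigma and HIV care outcomes. Model (2) is not built from these acts, and none of the simulations examined an arm contrast.

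Finally, a reader might infer that within-person estimation solves the problem. It does so only if activity is stable. Section 5.4.5 (Qualitative interviews) expects engagement to change over time, and under drift the fixed-effects model fails almost as often as the unlagged one. Person fixed effects also absorb arm, while 10.3.3 wants differences across the two treatment groups.

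The objection does not remove the core. If the active or passive score is the outcome, the overlap is direct. If visits or time is the outcome, differences in personal activity still produce the association, and section 1.2 reports that engagement varied greatly between participants in the earlier intervention.

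**Conclusion.** The concern holds for model (1) with participant-level metrics. As written, a strong same-window association is expected with no peer influence and cannot support a reading that network structure influences or affects engagement. The overlap is direct for the active and passive scores; visits and time on app are affected only through differences in personal activity. Model (2) and the primary analysis are outside it. This is one sub-model of a secondary aim: it should be corrected before analysis, but it does not threaten the trial's main result.

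The simulated sizes rest on assumed rates, spreads and reply targeting that the documents do not give. The direction held in every parameter set tried. The exact correlations, and the false-positive rates after partial remedies, did vary between sets and should not be taken as predictions for this trial.

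**What to change.** In section 10.3.3, for model (1):

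- **(a) Predictor.** Exclude the user's own outgoing acts. Use ties received from others in an earlier window.
- **(b) Outcome.** Use engagement in a later, non-overlapping window. Report a measure that forms no ties (log-ins, time on app, articles, quizzes) alongside forum engagement, and adjust for the user's own prior engagement.
- **(c) Reference.** Judge the association against a no-influence reference that keeps each user's activity in each window. For example, hold posts, replies, likes and reads fixed, permute who receives ties given posting volume, refit, and compare the observed coefficient with the permuted ones. Do not rely on person fixed effects alone. The simulations above did not test this reference, so it should be checked on simulated data before the plan is locked.
- **(d) Reporting.** Present same-window associations as descriptive only, and align the wording in the Study Abstract and section 5.4.1 with what model (1) can show.

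The cost is extra analysis and wider intervals. No new data are needed: Table 1 states that every user action is date- and time-stamped and already lists articles read and quizzes completed. The closing note of section 10.3.3 provides for documenting such changes in the Statistical Analysis Plan.

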10.4 Missing Data

Several procedures will be used to conduct data analysis when data for either outcomes or covariates are missing. The first step will be to assess the extent and pattern of missing data. If data are missing for only a few cases, then data analysis will be conducted only on study participants with complete data. However, when such a strategy would result in loss of data from a substantial proportion of participants, or if this approach would lead to biased or inaccurate results, then some form of imputation will be performed. The form of imputation used will depend on the nature of the data that are missing. For example, data that are collected repeatedly might be imputed using the "last value carried forward" method; and in some instances, interpolation between neighboring points might also be used.

When the primary endpoint is missing, one data analysis will be conducted using only cases with the endpoint. Subsequent analysis will be done where missing endpoints are imputed. Hot-deck imputation or regression imputation may also be used in this context.

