5.4 Intervention/Investigation Procedures

5.4.1. Randomized Trial Design

We will test whether a smartphone application (app) intervention (HMP Stigma) that promotes user-generated content and engagement to address intersectional stigma is associated with *successful engagement in care* as compared to an information-only control arm consisting of online informational articles and resources curated for YBLMT (Specific Aim 1). We will then examine how user engagement mediates the changes observed in stigma and HIV care outcomes across the 12-month follow-up period (Specific Aim 2). To describe how the social network composition of HMP Stigma affects user engagement and our HIV prevention and care outcomes across a 12-month follow-up period (Specific Aim 3), we will allow the composition of the intervention networks to vary. Participants randomized to Intervention Arm 1 will engage in a researcher-created network where half of the participants are HIV-positive. Participants randomized to Intervention Arm 2 will engage in a peer-referred network in which they may invite 2 peers (irrespective of race/ethnicity and/or HIV status) into the study. All participants who are randomized into Arm 2 will be HIV positive and we assume that peers they refer will be a mix of HIV-negative, HIV-positive, and HIV-unknown status.

5.4.2 HemaSpot Package, Delivery and Tracking: 120

At baseline and months 6 and 12, HIV-positive participants will be mailed a HemaSpot package which contains: 1) one HemaSpot kit with all necessary materials to perform a finger prick, a biohazard bag, and study labels; 2) an instructional booklet for how to properly collect a specimen for the HemaSpot device; 3) a return envelope addressed to the processing lab with pre-paid postage; and 4) a lab sheet which includes the participant's study ID. The U. Penn team will

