8.0 PARTICIPANT MANAGEMENT

8.1 Tracking Participants / Follow-up

A detailed retention plan (see "HMP SOP-Recruitment and Retention.docx") will draw on our prior successful protocols with hard to reach populations to achieve ≥80% retention rate for the 3month assessment.⁴⁷ In our experience, successful retention has several key elements. First, it is critical to obtain accurate follow-up contact information. We will use best practices to retain participants while being sensitive to undue disclosure of YBLMT participating in the study. One barrier to retention among youth is changing cell phone numbers. Study staff will include a reminder for participants in the 3-, 6-, and 9-month survey emails to update their email and SMS contact information if it has changed in the past 3 months. Every effort will be made to reduce attrition as retention is critical to our study efforts. In the event that participants do not respond complete a follow-up survey within 7 days of the first email and in-app request, they will receive a second email with the link and an in-app notification. A third attempt will be made before the study coordinator or Care Navigator calls participants. Correlates of missing data and attrition will be carefully examined. Participants who miss one or more follow-up assessments may still continue in the study. We will compare those who completed different follow-up interviews with those who did not on key predictors from the baseline assessment to check for possible sample bias. The use of the Expectation-Maximization algorithm in the longitudinal analyses will also aid to overcome missing data concerns when appropriate. 192,193

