10.2 Power Estimates

The primary outcome for the proposed trial is stratified by HIV status and defined as *successful* engagement in care. For HIV-positive participants at baseline, we define successful engagement in HIV care as consistent VS across the 12-month trial (per IOM guidelines²¹⁸). For HIV-negative

or sero-unknown at baseline, we define successful engagement in care as participation in routine HIV testing (2 HIV tests with at least 3 months apart from one another, per CDC guidelines²¹⁹). We define power as correctly identifying the difference in the proportions of YBLMT with serospecific engagement in HIV care within 12 months of each intervention arm (2 arms: HMP Stigma with researcher-created network, HMP Stigma with peer-referred network) to the control arm (Information Control), thus powering for 3 independent hypothesis tests. Our sample size calculations are based on pair-wise HIV-stratified comparisons of the 3 groups in terms of proportion of successful engagement using a two-sided significance level of 0.05 altered by the number of comparisons using a Bonferroni adjustment (significance level is 0.017 for 3 comparisons). To have 80% power to detect a minimum effect size (OR=1.9) of successful engagement in care between the 3-arm trial, we will require at least 450 HIV-negative and 450 HIV-positive participants to detect a 17% difference in successful engagement in. In the event of a 20% loss to follow-up, we will have sufficient power to detect an OR=2.1 (18% difference) at alpha=.017. Participants may continue the study even if they miss an assessment intermittently. We will compare those who completed different follow-up interviews with those who did not on key baseline predictors to check for possible sampling bias. Our analysis will use ITT as appropriate.

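### Section 10.4 leaves last value carried forward and interpolation open for the viral-load series, where either can turn a missing sample into consistent suppression

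*Combined protocol and SAP*

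**What the plan says.** Section 10.4 (Missing Data) applies "when data for either outcomes or covariates are missing". Imputation comes in when a complete-case analysis would lose a substantial share of participants or mislead. For repeatedly collected data, two examples are given, both conditional: "last value carried forward" "and in some instances, interpolation between neighboring points might also be used".

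The primary endpoint then has its own paragraph: "When the primary endpoint is missing, one data analysis will be conducted using only cases with the endpoint". A later analysis imputes missing endpoints, with hot-deck and regression imputation added as possibilities.

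For HIV-positive participants, section 10.2 states: "we define successful engagement in HIV care as consistent VS across the 12-month trial". Section 5.4.2 sets the sampling: "At baseline and months 6 and 12, HIV-positive participants will be mailed a HemaSpot package". No section says how many suppressed samples make suppression consistent, or how a missing sample is scored.

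Section 8.1 adds, where appropriate: "The use of the Expectation-Maximization algorithm in the longitudinal analyses will also aid to overcome missing data concerns". Section 10.3.3 plans generalized linear mixed models with maximum likelihood for the fixed effects.

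**The concern.** Viral load is an outcome collected repeatedly, so the two example methods are open for it. The primary-endpoint paragraph adds hot-deck and regression imputation but rules nothing out. For an endpoint about staying suppressed, filling a gap with a suppressed value assumes the persistence that the endpoint is meant to test. For the stigma surveys, carrying baseline forward imputes no change.

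The condition for imputation may well be met. Section 10.2 itself considers 20% loss, and the only numerical retention target, in section 8.1, is for month 3. Under section 5.4.2, an unusable specimen brings no replacement kit if the participant did not view the instructional video. Section 3.3.1 reports better outcomes among more engaged users in the earlier trial. Missing samples could therefore be related to outcome and could differ by arm. At stake are a shifted success rate in the imputed analysis of the HIV-positive stratum, a possible false difference between arms, and a standard error that is somewhat too small.

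**Working it through.** Section 10.4 gives no figure, so there is none to reproduce.

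**Step 1: which patterns change.** Write baseline, month 6 and month 12 as S (suppressed), U (unsuppressed) or _ (missing). Take success to mean SSS, which is an assumption.

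| Pattern | Carried forward | Interpolated |
|---|---|---|
| SS_ | success | still missing |
| S__ | success | still missing |
| S_S | success | success |
| any pattern with an observed U | failure | failure |
| baseline missing, no U | still missing | still missing |

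Carrying forward creates successes only among participants suppressed at every sample they gave. Interpolation needs a later sample, so it changes no dropout's score; it acts only on S_S.

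**Step 2: size of the bias from carrying forward.** The documents give no suppression rates, so these inputs are assumed:
- 65% are suppressed up to and including month 6.
- 85% of those observed at month 12 stay suppressed.
- A fraction k of those lost stay suppressed (0.85 or 0.60).
- A fraction m miss month 12. The value 20% matches the loss considered in section 10.2; 15% v 30% by arm is assumed.

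True rate = (1−m)×0.65×0.85 + m×0.65×k. Carried-forward rate = (1−m)×0.65×0.85 + m×0.65. Bias = m×0.65×(1−k).

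- m = 0.20, k = 0.85: 0.5720 − 0.5525 = 0.0195, or 2.0 points.
- m = 0.20, k = 0.60: 0.572 − 0.520 = 0.052, or 5.2 points.
- 15% v 30% missing, k = 0.85: 0.0146 v 0.0293, a false difference of 1.5 points.
- 15% v 30% missing, k = 0.60: 0.039 v 0.078, a false difference of 3.9 points.

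**Step 3: check with all three samples.** Take 150 HIV-positive participants per arm (section 3.2) and 30 dropouts, half lost after baseline and half after month 6. Assume baseline suppression s of 0.5 to 0.9 and a chance a of 0.8 to 0.9 of staying suppressed over each six months, the same for those lost. Excess successes = 15s + 15sa − 30sa².

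- Smallest (s = 0.5, a = 0.9): 7.5 + 6.75 − 12.15 = 2.1 participants, or 1.4 points of 150.
- Largest (s = 0.9, a = 0.8): 13.5 + 10.8 − 17.28 = 7.0 participants, or 4.7 points.

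Interpolation adds none among these 30.

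**Step 4: standard error.** Take n = 150, 65%, 85% and 20% missing at random.

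- Carried forward, treated as observed: √(0.572×0.428/150) = 0.0404.
- A valid estimate as a product of the two proportions, with month-12 data on 150×0.65×0.80 = 78 people: √(0.85²×0.65×0.35/150 + 0.65²×0.85×0.15/78) = √(0.001096 + 0.000691) = 0.0423.
- The ratio is about 0.956, so the carried-forward standard error is about 4% too small.

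**The case against.** The strongest reply is that nothing assigns these methods to the primary endpoint. They are examples, worded as possibilities and triggered only by substantial or biasing loss. The endpoint's own paragraph puts complete cases first and names other imputation methods. That stands: the bias arises only if carrying forward or interpolation is chosen for the later, imputed analysis. But the paragraph does not exclude that choice, and optional wording allows it to be made after the data are seen.

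Four stronger readings are tempting, and the documents or the arithmetic do not support them.
- A reader might infer that both methods count dropouts as successes. Interpolation never fills a dropout's visits, and under carrying forward a dropout with any observed unsuppressed sample remains a failure.
- A reader might infer that sections 8.1 and 10.4 contradict each other. Both are worded as non-exclusive options; they are unreconciled, not contradictory.
- A reader might treat all 20% of missing results as invented data and put the loss of standard error at 1−√0.80, or 11%. Participants already unsuppressed at month 6 are failures whatever month 12 shows. Only 0.20×0.65 = 13% are undetermined, so even the crude bound is 1−√0.87 = 6.7%.
- A reader might infer that the error always favours the arm with more loss. That needs the same chance of staying suppressed among those lost in both arms.

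It is also fair to say that multiple imputation is not the only remedy, and that section 10.3.3 already plans maximum likelihood for the mixed models.

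**Conclusion.** The concern holds in a limited form. Section 10.4 leaves two single-fill methods available for the HIV-positive primary endpoint's data, and one of them, carrying forward, would score people lost while suppressed as consistently suppressed. Under the illustrative rates, the overstatement at 20% loss is about 2 to 5 points within an arm. A false difference between arms of about 1.5 to 3.9 points needs the loss in one arm to be double that in the other. For scale, section 10.2 plans for differences of 17 to 18 points.

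These sizes rest on assumed suppression rates and on reading consistent suppression as every sample suppressed. The HIV-negative testing endpoint is not touched by this argument. The change is cheap and should be made, but the point does not show that the planned primary comparison is invalid.

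**What to change.** - In section 10.4, remove carrying forward and interpolation for outcomes.
- Define consistent suppression by the samples required, and state how a missing sample is scored, including when an observed unsuppressed sample already settles the result.
- For the imputed analysis of the primary endpoint, multiply impute the missing visit's viral-load result and derive the endpoint in each imputed data set. Report it beside the planned complete-case analysis and a sensitivity analysis that counts missing as failure.
- Fit the longitudinal mixed models by maximum likelihood to the visits observed, with no prior filling. Say in sections 8.1 and 10.4 which method governs which analysis.

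The cost is SAP wording, modest programming and slightly wider confidence intervals. No change to data collection is needed.
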